## 5.3 STRATEGIES FOR RECRUITMENT AND RETENTION

### ***Recruitment and Informed Consent***

To ensure adequate enrollment of an adequate number of participants, we will employ a number of recruitment strategies. First, Participants will be recruited from the University of North Carolina at Chapel Hill Outpatient Psychiatry Clinic, where the PI currently follows psychotherapy patients and therefore have access to recruitment pathways. Second, we will advertise to the Raleigh, Durham, Chapel Hill (i.e., the “Triangle”) community using email and listserv advertisements (sent to the UNC-Chapel Hill community), flyers in local businesses and buses, and radio/newspaper/website ads.

Potential participants will complete initial eligibility screening by telephone and a secure online questionnaire.

No more information will be asked of participants than necessary to obtain eligibility information and to contact those who appear to be eligible to schedule a screening/enrollment visit. At this initial visit, the PI ([name]) will obtain written informed consent for further screening regarding suicidality from those individuals who pass the initial telephone and questionnaire screenings and are interested in participating. This consent will inform participants regarding the nature of the questions to be asked. If the participant consents, the Self-Injurious Thoughts and Behaviors Interview and the Scale for Suicidal Ideation Interviews will be administered. If the participant is not eligible for the study following the screening (see details above), they will be dismissed and referred for treatment as necessary. If they are eligible, [name] will obtain additional written informed consent for participation in the larger study (i.e., the screening visit will become the enrollment visit). During the consenting process for the larger study, all of the applicable consent forms will be reviewed with each individual, and they will be given as much time as they would like to discuss their participation with their significant others and decide whether to participate.

### **INCLUSION OF WOMEN AND MINORITIES**

Men will not be included in this study, given the stated purpose of examining ovarian hormone withdrawal as a mechanism of suicidal risk in women. 45 women will be included in the study.

The UNC Center for Women’s Mood Disorders has a strong commitment to the enrollment of minority women in research projects, and this commitment will be reflected in this study. As shown below, the ethnic and racial composition of the population from which subjects will be recruited, including Orange, Durham, and Wake counties, is similar to the population of the United States as a whole.

Race/Ethnicity	Wake	Durham	Orange	Adjusted Average
White	70%	54%	78%	69%
Black or African American	21%	39%	12%	24%
American Indian/Alaska Native	1%	1%	1%	1%
Asian	6%	5%	7%	6%
Hispanic or Latino Origin	10%	14%	8%	11%

**The PI plans to recruit similar proportions of ethnic and racial minorities for the study. We have conservatively estimated our ability to recruit a sample that is 76% White, 20% Black or African American, 4% Asian, and with 8% identifying as Hispanic or Latina.**

Recruitment Plan for Minorities : We realize, however, that specialized efforts will be needed to meet these goals. Because minorities underutilize mental health care, the PI will also advertise in the community to recruit subjects who are currently experiencing emotional symptoms. [name], primary mentor, has a long-standing track record of successful recruitment of African Americans (our largest minority population) into clinical research studies. In her most recent ethnic differences research (RO1-DA13705), she was successful at recruiting over 125 African American men and women (50% of the entire sample) and in each of her current studies (RO1s MH087619 and MH099076), 30% of the women enrolled identify as African American. We will employ the strategies that have proven successful in her prior studies. The single most effective strategy involves the use of minority research staff in the recruitment and retention process. Other strategies involve the use of culturally sensitive language in advertisements, including assurances that the study involves no experimental drugs or devices. We will also advertise in periodicals targeting African American populations and work with community-based minority programs. Statistics will be kept throughout the study documenting recruitment strategy and enrollment rates, allowing the PIs to adjust initiatives accordingly. Should additional initiatives be necessary, we will work directly with leaders from the African American community.

## JUSTIFICATION FOR INCLUSION OF INDIVIDUALS WITH CURRENT SUICIDALITY

As reviewed in the study background and rationale, the purpose of the study is to examine the impact of natural perimenstrual hormone withdrawal (vs. prevention of hormone withdrawal/stabilization of E2/P4) on within-person changes in suicide risk. The present sampling strategy **ensures generalizability** of our findings to clinical populations of interest (i.e., not simply depressed women, but those with suicidality) and will also **prevent a floor effect** (i.e., zero-inflation of daily outcome measures and associated limitations in power to detect effects) on primary daily outcome measures (e.g., mediating behavioral constructs, suicidality).

Individuals with current suicidality **are not necessarily at imminent risk for suicidal crises/attempt** (i.e., their risk is manageable on an outpatient basis through frequent clinical contact, such as the daily calls in the present study). Because the hormone protocol simply prolongs the physiologic luteal hormone profile, it is not expected to expose participants to additional risk of suicidal crisis beyond what they would naturally experience during their typical monthly menstrual cycles. However, out of an abundance of caution, we will **exclude women with elevated imminent risk for suicidal crisis/attempt** (determined by structured interview and established guidelines). Individuals with histories of suicidality often have ongoing, habitual thoughts about death or suicide that are highly distinguishable from **imminent risk for suicide attempt**. In further support of this notion and of the feasibility of recruiting this population, it should be mentioned that up to 1/3 of the American population experiences suicidal ideation at some point in their lives, yet less than .01% die by suicide each year.

## RETENTION OF INDIVIDUALS WITH SUICIDALITY

Although a variety of exclusion criteria will be applied, the PI's recent work has prepared her to recruit, retain, and maintain the safety of women with suicidal ideation but low imminent risk of attempt. Furthermore, the majority of individuals with suicidal ideation do not evidence imminent risk for suicide attempt, supporting the feasibility of recruiting from this population. With regard to retention, the PI has demonstrated the capacity to recruit and retain women with BPD with suicidal ideation, and participants with BPD in her recent study have completed 85% of daily email surveys; given larger incentives for shorter daily contacts, we expect a higher response rate. The PI has also worked on recruitment and retention (using the same psychiatric exclusion criteria) in her new clinical fellow role with [name], who has great success in the recruitment, phone engagement, and retention of suicidal outpatients. Empirically-supported strategies for retention will include study branding, frequent contact, monetary rewards, and graduated compensation schedules.

### **Study subjects will receive the following monetary incentives:**

\$100 pay for one enrollment visit

\$50 pay for each laboratory testing session x 6 laboratory sessions = \$300 possible testing visit pay

\$200 pay for daily phone calls (prorated at \$5 per day if subject withdraws)

= For a total possible compensation of \$600

## 5.4 PARTICIPANT WITHDRAWAL OR TERMINATION

### 5.4.1 REASONS FOR WITHDRAWAL OR TERMINATION

Participants are free to withdraw from participation in the study at any time upon request. An investigator may terminate participation in the study if:

- Any clinical adverse event (AE), or other medical condition or situation occurs such that continued participation in the study would not be in the best interest of the participant as determined by the DSMB or [name] in collaboration with [name]

(severe mood deterioration, severe changes in suicidality), [name] (hormonal side effects). [name] may consult [name] with regard to gynecologic issues as necessary.

- The participant meets an exclusion criterion (either newly developed or not previously recognized) that precludes further study participation.

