#### 4.2.1 PRIMARY ENDPOINT

The primary endpoints (described below) of this mechanistic study are suicidal ideation and planning score differences between placebo days and stabilization days on the SITBI interview. These were chosen given their strong predictive validity in epidemiological studies.

- (1) Mean Within-Person Condition Difference (7 final placebo days – 7 final stabilization days) of SITB Suicidal Ideation subscale score
- (2) Mean Within-Person Condition Difference (7 final placebo days – 7 final stabilization days) of SITB Suicidal Planning subscale score

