## **SPECIFICS OF SUICIDE RISK-RELATED ELIGIBILITY CRITERIA**

The study will **include only women with current suicidal ideation** (past-month endorsement of suicidal ideation) in order to maximize generalizability to our clinical population of interest. We hypothesize that *natural* perimenstrual withdrawal from ovarian hormones will be associated with significant but **transient shifts in continuously-estimated suicide risk that are not expected to escalate to the level of suicidal crisis/attempt** (due to the exclusion of certain women at highest risk for attempt, as noted below). In order to minimize the risk of suicidal crises during the study, we will **exclude women who meet evidence-based criteria for imminent risk of acute suicidal crisis/attempt**.

*The goal of these exclusion/inclusion criteria is to minimize the risk that a participating woman will demonstrate imminent risk of suicidal crisis/attempt during the study. The determination of acceptably low current risk of suicidal crisis/attempt will be carried out in multiple steps, as follows:*

1. First, women must pass a phone screen in which they will report on their previous psychiatric diagnoses and recent history of suicide attempts. At that juncture, the following criteria will be applied:
  - a. A woman will be excluded if she reports a suicide attempt or any concrete suicidal planning in the past 3 months, as the majority of repeated attempts occur within the first three months following an initial attempt.
  - b. A woman will be excluded if she reports a history of more than one suicide attempt, as multiple attempts represent a uniquely potent risk factor for additional suicidal crises/attempts.
  - c. A woman will be excluded (and referred) if she reports that she does not currently visit a mental health provider (psychiatrist, therapist) at least once every 3 months.
  - d. A woman will be excluded if she reports any extreme external stressors (e.g., death of a loved one, loss of employment) in the past month, as extreme stressors drastically increase the risk of suicidal crisis.
  - e. A woman will be excluded if she reports a history of clinical diagnosis with manic episode, psychotic symptoms, or substance use disorder, as these disorders reduce predictability and increase likelihood of suicidal crises/attempt.

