## EXPERIMENTAL ELIGIBILITY TABLE

The goal of the suicide-related exclusion/inclusion criteria (outlined below) for the study is to **minimize** the risk that a participant will experience an acute suicidal crisis or attempt suicide during the study. Evidence-based criteria were developed in collaboration with the co-mentor, [name]. History of mania, psychosis, or substance abuse disorder will also be exclusionary. Table notes: Recent = In the past month. MHP = Mental Health Provider. SITBI items 3a, 3b, 4a, 4b, 4c. SITBI items 1a, 1b, 1c, 1f, 2c. SITBI items 2a, 2b.

ROW	Suicide Attempts 		Suicidal Thoughts 				Recency of Last Suicidal Planning 	Current Access to Means	Recent Stressors/Loss	Current Frequency of MHP Contact	Current Social Support
	Number	Recency	Recency	Recent Frequency	Recent Severity	Recent Intent					
1	Never	Never	In past year	Less than monthly	1f=1	2c=1	Never	No Access to Means	None	>1x/month	Multiple Strong Supporters
2 No more than 3 total positive findings allowed in Rows 2,3, +4	Any gesture or NSSI, no attempt	In past 2 years	In past month	~1x/month	1f=2	2c=2	>2 years ago		Extreme Stressors in past year	~1x/month	One Strong Supporter or multiple supports
3 No more than 2 total positive findings allowed in Rows 3 + 4	1 aborted attempt	In past year	In past week	~1x/ week	1f=3	2c=3	1-2 years ago	Access to Nonspecific or Unfeasible means	Extreme Stressors in last 3 months	~1/2 months	Very Limited Support
4 No more than 1 positive finding allowed in Row 4	1 attempt	In past 6 months	Now	>1x/ week	1f=4	2c=4	3 months to 1 year ago	Access to Specific, Feasible Means	Extreme Stressors in last 1-2 months	~1x/ 3 months	No Support
5 No positive findings allowed in Row 5	>1 attempt	In past 3 months					<3 months ago		Extreme Stressors in last month	<1x/ 3 months	

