#### 5.4.2 HANDLING OF PARTICIPANT WITHDRAWALS OR TERMINATION

**Protocol for Discontinuation and Referral.** If a participant shows emergence of severe mood symptoms or greater than low risk of suicide attempt, the UWRAP protocol for assessing and managing suicide risk will be closely followed, supervised by [name] and [name] (see Appendix for UWRAP). However, if a participant is judged to be at imminent risk of suicide and therefore in need of immediate hospitalization, the participant will be immediately discontinued from participation and hospitalized. Our offices are in close proximity to UNC emergency department, and participants requiring immediate emergency care can easily be transferred there. An immediate follow-up phone call to the participant's mental health provider alerting them to the change in symptoms (see information below regarding consent to provider-researcher communication) will occur immediately. If the participant is taking study medication currently, [name] will immediately be contacted and he will break the blind. If it is revealed that the participant is currently in the placebo condition, he will take no further action. However, if it is revealed that the participant was currently in an active hormone stabilization condition, he will oversee the subject's discontinuation of the exogenous hormone according to his best clinical judgment.

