#### 7.3.5 EARLY TERMINATION VISIT

Should early termination be deemed necessary (following procedures detailed above), and the situation does not involve a need for immediate hospitalization of the participant, then the participant will be invited to an early termination visit in which the full typical debriefing interview (i.e., risk assessment and referral as appropriate) will be conducted.

---

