## 7.8 RESCUE MEDICATIONS, TREATMENTS, AND PROCEDURES

Not Applicable.

Hospitalization will serve as a “rescue treatment” should imminent suicidal risk emerge.

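### Removal from the study can depend on the co-primary outcomes, no rating is required at or after removal, and an undefined carry-forward may let milder pre-crisis ratings stand for the condition in which the crisis occurred

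*Combined protocol and SAP*

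**What the plan says.** **Outcomes.** Section 4.2.1 defines the co-primaries as "suicidal ideation and planning score differences between placebo days and stabilization days on the SITBI interview". The second is "Mean Within-Person Condition Difference (7 final placebo days – 7 final stabilization days) of SITB Suicidal Planning subscale score". Section 4.1 has a shortened SITBI collected on every daily call. Section 10.4.2 averages the calls in the final seven days of each condition and compares the two means with a paired t-test, or a nonparametric counterpart if assumptions fail.

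**Removal.** Section 5.4.1 lets an investigator end participation for an adverse event or situation that makes continuing contrary to the woman's interest, and names severe changes in suicidality within that ground. A second ground is "The participant meets an exclusion criterion (either newly developed or not previously recognized) that precludes further study participation". Section 5.4.2 manages risk that is above low under the UWRAP. At imminent risk with need for hospitalization, "the participant will be immediately discontinued from participation and hospitalized". Section 7.8 adds: "Hospitalization will serve as a “rescue treatment” should imminent suicidal risk emerge".

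**Measurement afterwards.** Section 7.3.5 invites a terminated woman to a closing risk assessment only if "the situation does not involve a need for immediate hospitalization of the participant". Section 6.1.8 provides follow-up until clinical care is in place, with no outcome rating. Section 8.3 records significant deterioration as an adverse event.

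**Analysis.** Section 10.3 specifies an intent-to-treat dataset with a carry-forward approach but does not say what value is carried, or from where. Section 6.1.9 refers instead to multilevel models on all patch and pill days. Section 10.1 states that there will be no formal SAP.

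**Planning at entry.** The suicide-risk eligibility text in 5.1, item 1a, reads: "A woman will be excluded if she reports a suicide attempt or any concrete suicidal planning in the past 3 months". Planning less than 3 months ago is in Row 5 of the Eligibility Table, where the rule is "No positive findings allowed in Row 5".

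**The concern.** The event that ends follow-up is an extreme value of what the trial measures. Section 10.2 predicts larger perimenstrual increases in suicidality under placebo. If that is right, removals for suicidality fall more often in the placebo condition, and the plan has no rule that keeps their severity in the endpoint. A woman removed in her first condition also never supplies the second. The expected result is a placebo-minus-stabilization difference pulled toward zero on both co-primaries.

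Planning is the more exposed outcome. Entry rules keep out recent planners, so non-zero planning scores may come from few women. The text does not settle whether planning that first appears on study is simply an outcome, also a ground for ending participation, or both.

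**Working it through.** **1. What happens to the ratings, on the text alone**

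| Situation | Participation | Rating required at or after removal |
|---|---|---|
| Risk above low, not imminent (5.4.2) | UWRAP; no automatic removal | Daily calls continue |
| Severe change in suicidality (5.4.1) | May be ended | Early-termination assessment is offered; daily ratings are not continued |
| Imminent risk, immediate hospitalization (5.4.2, 7.8) | Ended | None; 7.3.5 does not apply |

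Calls made before removal exist. The gap is at and after removal, and in how the event enters the seven-day mean. A woman removed before the final seven days has no rating in that window. One removed within it has a mean over fewer, earlier days.

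**2. Illustration by deletion of affected pairs**

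The plan has no figure to reproduce here. Section 10.5 allows for attrition of 25%, and its 45 randomized for 30 completers implies 1 − 30/45 = 33%, but neither is split by reason. All event rates below are therefore assumptions.

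Inputs: d = .40 (10.5), taken as the standardized paired difference; within-woman correlation ρ assumed to be .5, .7 or .8; normal scores with SD 1. The placebo mean exceeds the stabilization mean by δ = d × √(2(1 − ρ)):

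- ρ = .5: .40 × 1.000 = .400
- ρ = .7: .40 × .775 = .310
- ρ = .8: .40 × .632 = .253

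A pair is deleted when either score exceeds the level that 5% or 10% of placebo scores exceed. The results, from 4,000,000 simulated pairs for each ρ, are fractions of the true value:

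| Placebo crossing rate | ρ | Women lost | Raw mean difference | Standardized effect |
|---|---|---|---|---|
| 5% | .5 | 6.4% | .923 | .961 |
| 5% | .7 | 6.3% | .947 | .973 |
| 5% | .8 | 6.1% | .960 | .980 |
| 10% | .5 | 12.8% | .874 | .934 |
| 10% | .7 | 12.4% | .912 | .954 |
| 10% | .8 | 12.1% | .933 | .965 |

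The standardized effect falls less than the raw mean because cutting off the upper tail also shrinks the SD of the differences. With 30 analysed pairs and a two-sided paired t-test at .05, power for d = .40 is .56 without removals, .53–.55 at the 5% rate and .51–.53 at 10%.

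**3. Illustration by carry-forward**

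Deletion is not what 10.3 describes. A second simulation used d = .60 (also from 10.5), ρ = .5 or .7, and half the women placebo first. A woman lost in her first condition has that value carried into the second, so her difference is 0. A woman lost in her second condition is given a pre-crisis value for it. Fraction of the raw mean difference kept:

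| Placebo crossing rate | Pairs deleted | Pre-crisis value carried | Triggering value kept |
|---|---|---|---|
| 2% | 97–98% | 95–96% | 97–98% |
| 5% | 93–95% | 89–90% | 94–95% |
| 10% | 89–92% | 80–83% | 89–90% |

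Power for 30 pairs at d = .60 is .89 without removals. With pre-crisis values carried it is .84–.85 at the 5% rate and .78–.80 at 10%. Pre-crisis carry-forward therefore attenuates more than deletion. Keeping the triggering value recovers part of the loss: from 80–83% to 89–90% at the 10% rate.

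**4. Planning: the passages side by side**

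Item 1a is applied at the phone screen and re-applied at enrollment. The 5.2 list applies at baseline and does not include planning. The eligibility text nevertheless says that planning excludes, and 5.4.1 covers newly developed exclusion criteria without exempting the suicide-related ones. Section 5.4.2 sends non-imminent risk to the UWRAP. The text supports more than one reading.

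**The case against.** A reader might infer three stronger things, and the documents do not support them.

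- *The most severely affected women drop out of the contrast.* Section 10.3 keeps them nominally in an intent-to-treat set by carry-forward. What is missing is a defined value, not necessarily the woman.
- *A hospitalized woman leaves no rating.* Daily SITBI ratings up to the crisis exist, possibly including the call that triggered removal. Only the closing assessment is withheld.
- *Any planning reported on study leads to removal, so the planning difference is zero by construction.* Item 1a is a screening and enrollment rule, 5.4.1 is permissive and limited to criteria that preclude continuing, and 5.4.2 manages non-imminent risk without removal. Planning reported on a call is also rated that day.

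The size can fairly be challenged too. The protocol does not expect the shifts in risk to reach crisis or attempt, so 10% may be far too high, and at 5% the standardized effect keeps 96–98% under deletion.

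These points limit the finding but do not remove it. Severe changes in suicidality are an express ground in 5.4.1, so outcome-dependent loss does not rest on the planning inference. Being kept nominally with a pre-crisis value can be worse than being deleted.

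**Conclusion.** The concern holds in this form: loss can depend on the co-primary outcomes, no rating is required at or after removal, and the undefined carry-forward may replace the worst outcomes with milder earlier ones. The direction is toward the null if the hypothesis is true.

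The size cannot be established from the documents. Under deletion, at d = .40 with normal scores and ρ of .5 to .8, the raw difference keeps about 92–96% at a 5% placebo crossing rate and 87–93% at 10%; the standardized effect keeps about 96–98% and 93–97%. Pre-crisis carry-forward was examined only at d = .60 and attenuates more. Normality is a convenience: 10.4.1 itself doubts it, and these figures should not be read as estimates for planning, where scores may be mostly zero.

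Whether on-study planning is an outcome, a ground for removal, or both is an ambiguity to be reconciled, not a demonstrated conflict. This is a worthwhile change at modest cost; it does not invalidate the design.

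**What to change.** Reconcile 4.2.1, the suicide-related eligibility rules in 5.1 (item 1a and Row 5), 5.4.1 and 5.4.2, so that the status of planning arising on study is explicit. The clinical decision stays with the responsible clinicians. Whatever they decide:

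1. In 5.4.2 and 7.3.5, separate ending study agent from ending data collection. Seek daily ratings and the early-termination SITBI from every discontinued woman who agrees, when clinically feasible, and flag days after agent was stopped.
2. Record the short-form SITBI ideation and planning items at the contact that leads to removal, and count them as that day's rating in that condition. This must be written in, because the protocol does not say that the UWRAP yields SITBI scores.
3. Report discontinuations and hospitalizations for suicidality by condition. Add a sensitivity analysis that ranks the paired difference of a woman hospitalized in a condition as most extreme against that condition, including when the other condition is missing. Ranking the difference, rather than the score within one condition, keeps a woman lost in her first condition in the test.

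With no separate SAP, these rules belong in the protocol, beside a definition of the carry-forward in 10.3. The cost is wording, a few SITBI items, a few extra calls and one sensitivity analysis. The main limitation is that ratings after agent is stopped no longer reflect the assigned hormone state, hence the flag.
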